#### Section 8: Screening questions for stigma

	Please indicate how strongly you agree or disagree with the following statements.		
SQS 1	"I would be ashamed if someone in my family had HIV"	Strongly agree; agree; disagree;      Strongly disagree	1;2;3;4
SQS 2	"I would not like to sit close to someone living with HIV, for	Strongly agree; agree; disagree;      Strongly	1;2;3;4

	example on public transport, at church or in a waiting room”	disagree	
SQS 3	“People living with HIV should not share cups”	Strongly agree; agree; disagree; Strongly disagree	1;2;3;4
SQS 4	“People living with HIV should not have sex”	Strongly agree; agree; disagree; Strongly disagree	1;2;3;4
SQS 5	“People living with HIV should not get pregnant/have children”	Strongly agree; agree; disagree; Strongly disagree	1;2;3;4
SQS 6	“people who test for HIV using self-testing should not disclose their HIV status”	Strongly agree; agree; disagree; Strongly disagree	1;2;3;4

Section 9: Decision making			
Variable name	Questions	Options	Option codes
DM_1	Whom would you consider to be main source of income in your house/relationship?	My partner/spouse; Myself; Both my partner/spouse and I, parents, other	1; 2; 3,4,5
DM_2	Given the total income in your house, roughly what is the percentage of your own contribution?		
DM_3	Do you make major decisions about how money is spent in your household?	No; Yes (someone else's approval needed); Yes (no one else's approval needed)	0; 1; 2

DM_4	Who makes decisions about how money is spent on a daily basis?	My partner/spouse; Myself; Both my partner/spouse and I, parents, other	1; 2; 3; 4; 5
DM_5	Who usually has more say about other important decisions in your relationship/house?	My partner/spouse; Myself alone; Both my partner/spouse and I; other people not including me, other people jointly with me	1; 2; 3; 4; 5
Section 10: Couple communication on sex			
CCS_1	Can you communicate with your partner about when to have sexual intercourse?	Never; sometimes; always	1; 2; 3
CCS_2	Can your partner communicate with you about when to have sexual intercourse?	Never; sometimes; always	1; 2; 3
CCS_3	Does your partner take into account your feelings about your sexual desires?	Never; sometimes; always	1; 2; 3
CCS_4	Do you feel comfortable talking with your partner about your sexual relationships?	Yes, no; sometimes/it depends	1; 2; 3
CCS_5	In your sexual relationship with your partner, who usually has more say about whether you have sex or not?	My partner/spouse; Myself; Both my partner/spouse and I	1; 2; 3
Section 11: Sexual relationships and power			
SRP_1	Please indicate how you feel about the following statements		
SRP_2	If I asked my partner to use a condom, he would get violent	Strongly agree; Agree; Disagree; Strongly Disagree	1; 2; 3; 4
SRP_3	If I asked my partner to use a condom, he would get angry	Strongly agree; Agree; Disagree; Strongly Disagree	1; 2; 3; 4
SRP_4	Most of the time, we do what my partner wants to do	Strongly agree; Agree; Disagree; Strongly Disagree	1; 2; 3; 4
SRP_5	When my partner and I disagree, he/she gets his/her way most of the	Strongly agree; Agree; Disagree; Strongly Disagree	1; 2; 3; 4

	time		
SRP_6	My partner has more say than I do about the important decisions that affect our relationship	Strongly agree; Agree; Disagree; Strongly Disagree	1; 2; 3; 4
SRP_7	My partner always wants to know where I am	Strongly agree; Agree; Disagree; Strongly Disagree	1; 2; 3; 4
SRP_8	A woman's most important role is to take care of her home and cook	Strongly agree; Agree; Disagree; Strongly Disagree	1; 2; 3; 4
SRP_9	My partner does what he/she wants even if I tell him/her not to	Strongly agree; Agree; Disagree; Strongly Disagree	1; 2; 3; 4
SRP_11	Men don't talk about sex, they just do it	Strongly agree; Agree; Disagree; Strongly Disagree	1; 2; 3; 4
SRP_12	My partner would be angry if I asked him/her to test for HIV	Strongly agree; Agree; Disagree; Strongly Disagree	1; 2; 3; 4
SRP_13	A man should have the final word about decisions in a relationship/home	Strongly agree; Agree; Disagree; Strongly Disagree	1; 2; 3; 4
SRP_14	I feel trapped or stuck in our relationship	Strongly agree; Agree; Disagree; Strongly Disagree	1; 2; 3; 4
SRP_15	In general, my partner has more power than I do in our relationship	Strongly agree; Agree; Disagree; Strongly Disagree	1; 2; 3; 4

**Follow-up questionnaire secondary distribution cohort - for secondary distributor  
(individuals given an HIVST for distribution to their partner)**

Use of HIV test kits (Question for secondary distributor)			
Variable Name	Question	Options	Option Codes
Use_HIVST 1	What was the date that you collected the HIVST for your partner?	Year; month; day	
Use_HIVST 2	When you collected the HIVST for your partner did you also collect an extra test for your own use?	No; Yes	0; 1
Use_HIVST 3	Did you give your partner an HIV self-test kit that you collected on his behalf?	No; Yes	0; 1
Use_HIVST 3a	If no, why did you not give the HIVST to your partner?	I lost the kit; my partner already knows his/her HIV positive status; I feared my partner would get angry; my partner has been away from the time I collected the test kit; my partner and I are no longer in partnership; other (Specify); refuse to respond	1; 2; 3; 4; 5; 6; 7
Use_HIVST 4	Did your partner use the HIV self-test that you gave him?	Yes – I was present when he used the self-test; Yes – I was told that the self-test kit was used; No- he did not use the self-test kit; I Don't know	1; 2; 3; 4
Use_HIVST 5	What was the date that your partner used	Year; month; day	

	the HIV self-test kit?		
Use_HIVST 6	When your partner used the self-test, did you also use a self-test at the same time?	Yes (Couple testing); No; Don't know	1; 2; 3
Use_HIVST 7	What were the results of your self-test?	HIV-positive; HIV-negative; Indeterminate; Don't know; Refused to answer	1; 2; 3; 4; 5; 6
Use_HIVST 8	Do you know the results of your partner's HIV test?	No; Yes; Don't know; Refused to answer	1; 2; 3; 5
Use_HIVST 9	What was your partner's test result?  Interviewer: Remind participant that they do not have to answer this question if uncomfortable. If she says that she knows but doesn't want to share – this is code 99. If the person tested but did not share the result with them so they don't know, this is code 98	HIV-positive; HIV-negative; Indeterminate; Don't know; Refused to answer	1; 2; 3; 4; 5
Use_HIVST 10	Did your partner go to a clinic or health facility in order to confirm the result that was obtained from the self-test (confirmatory testing)?	No; Yes; Don't know	0; 1; 2
Use_HIVST 11	Did your partner go to a clinic or health facility for HIV care?	No; Yes; Don't know	0; 1; 2
Use_HIVST 122	Is your partner currently in ART care?	No; Yes; Don't know	0; 1; 2
Use_HIVST 13	Did your partner go to the clinic or health facility for HIV prevention services?	No; Yes; Don't know	0; 1; 2
Use_HIVST 14	What HIV prevention services did they go for?	VMMC; to collect condoms; other (specify)	0; 1; 2

Social Harms/benefits Screening at follow-up visit			
Variable Name	Question	Options	Option Codes

SHS_Fu_1	When you gave your partner the HIV test kits, did you explain that it is for HIV testing?	Yes; No; Don't know	1; 2; 3
SHS_Fu_2	Has anything good happened to you or in your relationship which you think was a result of you talking about HIV testing or giving the test to your partner	Yes; No; Don't know	
SHS_Fu_2a	If yes; What was good? ( tick all that are relevant)	Discussed HIV; Was able to tell my partner my HIV status; Know my partners HIV status; Felt more comfortable with my partner; Felt more able to discuss issues with my partner; My partner was more loving/caring; Resolved some of our issues in our relationship Other ( free text)	
SHS_Fu_3	From the time your partner received the HIV self-testing kit, Has your partner ever.....		
SHS_Fu_3a	Pushed, grabbed, slapped, choked, hit or kicked you?	Yes; No; Don't know	1; 2; 3
SHS_Fu_3b	Threatened to hurt you, your children or someone close to you?	Yes; No; Don't know	1; 2; 3
SHS_Fu_3c	Insulted you or made you feel bad about yourself?	Yes; No; Don't know	1; 2; 3
SHS_Fu_3d	Taken away money or resources that you/your children need to survive?	Yes; No; Don't know	1; 2; 3
SHS_Fu_3e	Threatened to divorce you?	Yes; No; Don't know	1; 2; 3

SHS_Fu_3f	Sent you back to your family home?	Yes; No; Don't know	1; 2; 3
SHS_Fu_3g	Forced you to have sex when you did not want to?	Yes; No; Don't know	1; 2; 3
SHS_Fu_4a	[If yes to any of the above GBV questions] Did this happen as a result of discussing HIV testing with your partner?	Yes; No; Don't know	1; 2; 3
SHS_Fu_4b	Do you think any of these things were the result of having offered an HIV self-test to your partner?	Yes; No; Don't know	1; 2; 3

**Follow-up questionnaire for secondary distribution cohorts – questionnaire for intended user of secondary distribution HIVST kit**

Section 0: Preparing for the survey			
Variable Name	Question	Option	Option codes
PS 1	What is the date today?	[time stamp]	
PS 1a	CLINIC NAME	[EDC CODE]	
PS 2	Scan participant barcode		
PS 3	Which community are you in?	Community 1	1
		Community 2	2
		Community 3	3
		Community 4	4
		Community 5	5
		Other	Specify
PS 4	What models of HIV self-testing distribution are in this community? [tick all that applies]	VMMC	1
		Community- or facility led	2
		Secondary distribution through ANC	3
		Secondary distribution through ARTHIV testing and treatment services	4
		Workplace	5
		Other (Specify)	6
PS 5	Through which distribution model was the client offered an HIV self-testing kit?	Secondary distribution through ANC	3
		Secondary distribution through ART	4

Section 1: Consenting Process			
Variable Name	Question	Option	Option codes
Consent 1	I would like to take some time to explain the research that we are carrying out in this study about HIV self-testing.  At the end of my explanation, you can decide whether you would like to participate and continue with answering specific questions for the study. Before we begin, do you have any questions?		
Consent 2	Obtain consent using the consent form written in the language that the participant understands		
Consent 3	DID THE INDIVIDUAL GIVE CONSENT TO PARTICIPATE IN THE STUDY?	Yes	1
		No	2
Consent 4	WHAT WAS THE MAIN REASON THE PARTICIPANT DID NOT CONSENT?	Time constraints	1
		Confidentiality concerns	2
		Spouse would not agree	3
		Did not want to	4
		Unspecified reason	5
		Other (Specify)	
Section 2: Demographics			
	Today's date	Auto complete by EDC	
Demo 1	Sex	Male; Female	1;2
Demo 2	What is your date of birth?	DDMMYYYY	010119999 if unknown

Demo 3	How long have you been living in [NAME OF CURRENT PLACE OF RESIDENCE]?		
Demo 4	How many minutes did it take you to come to the health facility?	TIME (minutes)	
Demo 5	What form of transport did you use?	Came on foot	
		Taxi	
		Private car	
		Bus	
		Bicycle	
		Other	
Demo 6	What is the highest level of education you have completed?	No education; Grade 1;Grade 2;Grade 3;Grade 4;Grade 5;Grade 6;Grade 7;Grade 8 Grade 9 ;Grade 10 ;Grade 11 ;Grade 12;College;University;Don't know/Refuse	0;1;2;3;4;5;6;7;8;9;11;12;13; -1

Demo 7	How can you best describe your main income generating activity or work status?	Farmer (own land); Farm work on employer's land; Domestic; Work in bar, hotel, guest house; Fishing; Mining; Working in shop; Informal Selling; Commercial sex work; Transport (trucker, taxi driver); Factory; Guard (security company); Police/soldier; Clerical and office work; Government; Teacher; health care; Other Professional; Other (Specify)	
Demo 8	What is your religion?	Roman Catholic; Anglican; Seventh-Day Adventist; Baptist; Pentecostal; Salvation Army; Lutheran; Evangelical church; United Methodist/African Methodist; Jehovah's witness; New Apostolic church (NAC); Apostolic faith Mission (AFM); Zion Christian Church (ZCC); Other (Specify)	

Demo 9	What is your current marital status?	Single/never married; married/living together as if married; separated/divorced ; widowed	1;2;3;4
Demo 10	Do you currently have a main/primary sexual partner?	No; yes	0;1
Demo 11a	How would you describe your relationship with this sexual partner?	Husband/wife (married or living as married); Boyfriend/girlfriend; casual partner; One-time partner	1; 2; 3; 4
Demo 12	Did you come alone to the facility or you came with your partner	Alone; With my partner	1; 2

Section 3: Use of HIVST kit			
Use_ HIVST-_IU 1	Did you receive an HIV self-testing kit from your partner?	No; Yes	0;1
Use_ HIVST-_IU 2	Before your partner gave you the HIVST, had you ever heard of HIV self-testing?	No; Yes	0;1
Use_ HIVST-_IU 3	Before your partner gave you the HIVST, had you ever used an HIV self-test?	No; Yes	0;1
Use_ HIVST-_IU4	When did you receive an HIVST from your partner?	MMYYYY	
Use_ HIVST-_IU5	Did you use the HIVST kit?	No; Yes	0;1
Use_ HIVST-_IU 6	If you did not use the test kit, what are some of the reasons why you did not? Please tick all that applies	Too busy; did not know how to use; feared getting the results; already	

		know my HIV-positive status	
Use_HIVST_IU 7	When did you use HIVST kit? If you can't remember please give your best guess	Year; month; day	
M_HIV_Test_IU 8	If you don't mind, what was the result of your HIV test using the test kit that you were given by your partner?	Reactive; non-reactive/negative; I don't know; I can't disclose	1; 2; 3; 4
Section 4: History of HIV testing			
H_HIV_Test_IU 1	I would like to ask you questions about your history of HIV testing. [if you used an HIVST from your partner, this is the time before you received the HIVST kit from your partner]		
H_HIV_Test_IU 2	Before receiving an HIV self-testing kit from your partner, had you ever tested HIV?	No; Yes	0;1
H_HIV_Test_IU 3	Please indicate yes to the following statements if they indicate the reasons why you have never tested for HIV and no if they do not  I have never tested for HIV before because:	No; Yes	0;1
H_HIV_Test_IU 3.1	I am not at risk of being HIV positive	No; Yes	0;1
H_HIV_Test_IU 3.2	I do not want to know my status	No; Yes	0;1
H_HIV_Test_IU 3.3	I'm afraid of testing positive	No; Yes	0;1
H_HIV_Test_IU 3.4	I'm afraid of stigma and discrimination from testing for HIV	No; Yes	0;1
H_HIV_Test_IU 3.5	My partner won't let me test	No; Yes	0;1

H_HIV_Test_IU 3.6	Other family won't let me test	No; Yes	0;1
H_HIV_Test_IU 3.7	I do not have money to test	No; Yes	0;1
H_HIV_Test_IU 3.8	I cannot take time off work to test	No; Yes	0;1
H_HIV_Test_IU 3.9	It's not a dignified thing to do at my age	No; Yes	0;1
H_HIV_Test_IU 3j	It's not a dignified thing to do at my age	No; Yes	0;1
H_HIV_Test_IU 3.10	It's not a dignified thing to do at my age	No; Yes	0;1
H_HIV_Test_IU 3.11	The health facilities offer poor quality services, including lack of confidentiality	No; Yes	0;1
H_HIV_Test_IU 3.12	I do not trust health providers	No; Yes	0;1
H_HIV_Test_IU 3.13	I do not feel sick enough	No; Yes	0;1
H_HIV_Test_IU 3.14	Other reason	Specify	
H_HIV_Test_IU 3.15	Of the reasons for not testing for HIV, what is the main reason you have not HIV-tested?	OPTIONS from selections picked	
H_HIV_Test_IU 4	When did you last test for HIV?	DDMMYYYY	
H_HIV_Test_IU 4	What was the result of your last HIV test?	Reactive/ positive; non-reactive/negative; I don't know; I can't disclose	1; 2; 3; 4
H_HIV_Test_IU 6	Over the past 12 months, during your relationship with your partner, do you	Yes – I know with another spouse;	1;2;3;4;5

	know or suspect that your partner was having sex with someone else?	Yes – I know with another partner or partners; Yes - I believe there was another partner or partners; No, I know this partner did not have other partners; Don't know/No answer	
H_HIV_Test_IU 7	If you consider your behavior (current or past) with respect to getting HIV (including anything entirely due to a sexual partner you are/were with) - would you consider that you have been at high risk of HIV?	Very high; somewhat high; somewhat low; very low	
Section 4: Motivators of HIV testing			
	When offered an HIVST by your partner, did any of the following encourage you to test		
M_HIV_Test_IU 1	I tested because it was convenient and easy for me to self-test than to test at the clinic	No; Yes	0; 1
M_HIV_Test_IU 2	I have never had an HIV-test and wanted to learn my status	No; Yes	0; 1
M_HIV_Test_IU 3	I had never used an HIV self-test and wanted to use one	No; Yes	0; 1
M_HIV_Test_IU 4	I recently tested HIV negative and wanted to re-check	No; Yes	0; 1
M_HIV_Test_IU 5	I recently tested HIV positive and wanted to confirm my status		
M_HIV_Test_IU 8	I was sick and suspected it was because of HIV	No; Yes	0; 1
M_HIV_Test_IU 9	HIV is very common in this community so I thought I might be positive	No; Yes	0; 1
M_HIV_Test_IU 10	I thought my current/past sexual behaviour put me at high risk of getting HIV	No; Yes	0; 1

M_HIV_Test_IU 11	Many people I know have tested for HIV so I wanted to test as well	No; Yes	0; 1
M_HIV_Test_IU 12	I wanted to be able to get treatment without delay if I tested and was HIV-positive	No; Yes	0; 1
M_HIV_Test_IU 14	I accepted as I had no reason to decline	No; Yes	0; 1
M_HIV_Test_IU 15	I accepted because my partner wanted me to test	No; Yes	0; 1
M_HIV_Test_IU 16	I accepted because my partner forced me to HIV self-test	No; Yes	0; 1
M_HIV_Test_IU 17	I accepted to test because my wife is pregnant so I wanted to protect the health of my wife and baby	No; Yes	0; 1
M_HIV_Test_IU 18	I have or I have had an HIV positive sexual partner and I wanted to know my status	No; Yes	0; 1

#### Section 5: Questions about Alcohol and drug use

Alcohol_0	I will now ask you questions about drinking alcohol and drug use. I know these questions are sensitive and want to remind you that your answers are completely confidential. Do you have any questions before we begin?		
Alcohol_1	How often do you have a drink containing alcohol?	Never; Monthly or less; 2 to 4 times a month; 2 to 3 times a week; 4 or more times a week	1; 2; 3; 4; 5
Alcohol_2	How many drinks containing alcohol do you have on a typical day when you are drinking?	1 or 2; 3 or 4; 5 or 6; 7, 8, or 9; 10 or more	1; 2; 3; 4; 5
Alcohol_3	How often do you have six or more drinks on one occasion?	Never; Less than monthly; Monthly; Weekly; Daily or almost daily	1; 2; 3; 4; 5
Alcohol_4	How often during the last 12 months	Never; Less than	1; 2; 3; 4; 5

	have you found that you were not able to stop drinking once you had started?	monthly; Monthly; Weekly; Daily or almost daily	
Alcohol_5	How often during the last 12 months have you failed to do what was normally expected from you because of drinking?	Never; Less than monthly; Monthly; Weekly; Daily or almost daily	1; 2; 3; 4; 5
Alcohol_6	How often during the last 12 months have you needed a first drink in the morning to get yourself going after a heavy drinking session?	Never; Less than monthly; Monthly; Weekly; Daily or almost daily	1; 2; 3; 4; 5
Alcohol_7	How often during the last 12 months have you had a feeling of guilt or remorse after drinking?	Never; Less than monthly; Monthly; Weekly; Daily or almost daily	1; 2; 3; 4; 5
Alcohol_8	How often during the last 12 months have you been unable to remember what happened the night before because you had been drinking?	Never; Less than monthly; Monthly; Weekly; Daily or almost daily	1; 2; 3; 4; 5
Alcohol_9	Have you or someone else been injured as a result of your drinking?	No; Yes, but not in the last year; Yes, during the last year	0; 1; 2
Alcohol_10	Has a relative or friend or a doctor or another health been concerned about your drinking or suggested you cut down?	No; Yes, but not in the last year; Yes, during the last year	0; 1; 2
Alcohol_11	Among people of similar age and sex as you in this community during an average month, how common do you think it is for them to have six or more drinks on one occasion?	Very common; somewhat common; somewhat uncommon; very uncommon	1; 2; 3; 4
Drugs_1	In your lifetime have you ever used any drugs recreationally?	No; Yes	0; 1
Drugs_2	In the last 12 months, have you used drugs recreationally?	No; Yes	0; 1
Drugs_3	In the last 12 months, which drugs have you used?	Cannabis/Marijuana; Cocaine/Crack; Khat/Miraa; Ecstasy/Disco biscuit; Heroin; Amphetamine/Speeed; Tik; Nyamba (any)	; 2; 3; 4; 5; 6; 7

		drug mixed with ART and smoked); Glue/solvents/petrol sniffing; Other (Specify)	
Section 6: Linkage to HIV care (Only for those who self-test HIV positive)			
Link_HIV_Care 1	After self-testing HIV positive, did you go to the clinic to confirm your results?	No; Yes	0; 1
Link_HIV_Care 2	What was result of your confirmatory test?	Negative; Positive; I don't know; Refuse to respond	1; 2; 3; 4
Link_HIV_Care 3	After confirming your HIV-positive status, did you register at the clinic for HIV services?	No; Yes	0; 1
Link_HIV_Care 4	If yes, what date did you register for HIV care?	MMYYYY	[01011900 if UNKNOWN]
Link_HIV_Care 5	At which clinic did you register for ART care?	At the clinic in my community; At another clinic outside my community; at a private clinic	1; 2; 3
Link_HIV_Care 6	At the clinic, were you given the result of a CD4 cell count test?	No; Yes; Don't know/Refused	0;1; -1
Link_HIV_Care 7	If yes, do you know the result of your last CD4 cell count test?	No; Yes	0; 1
Link_HIV_Care 8	What was the CD4 count result?		
Link_HIV_Care 9	Why did you not register at a clinic for HIV care?	Not ready; clinic too far from home;	1; 2; 3
Link_HIV_Care 10	Have you started taking ART treatment?	No; Yes	0; 1

Link_HIV_Care 11	When did you start taking ART?	DDMMYYYY	
Link_HIV_Care 12	Do you know people who are taking ART?	No; Yes	0; 1
Link_HIV_Care 8 1	Who was it you knew, who had been on ART? Please choose all that apply from:	Sexual partner; Household member(s) (not including sexual partner); friend(s)/neighbour(s)/colleague(s); other	1; 2; 3; 4
Link_HIV_Care 9	Have you disclosed your HIV status to anyone, except to me for the purpose of this study?	No; Yes	0; 1 If No skip to Link_HIV_Care 5
Link_HIV_Care 10	To whom did you disclose your HIV status?	husband/wife /Sexual partner; Family Member; Friend/neighbour/colleague; Religious leader/; Health care; Other	1; 2; 3; 4; 5
Link_HIV_Care 11	What are the reasons why you did not register for ART care?	The clinic is too far; The hours of the clinic don't suit me; I did not have transport to go the clinic; I'm not interested in ART	1; 2; 3; 4;
Link_HIV_Care 12	Do you have your ART/HIV care card number?	Record number preferably from card; Card not available; Did not agree	1; 2; 3
Section 7: For partners reporting an HIV negative test result			
Link_HIV_Care 13	After your unreactive HIV self-test, did you go to the clinic to access HIV-related services?	No: Yes	0; 1

Link_HIV_Care 14	What services did you access?		
Link_HIV_Care 15	After your HIV negative result, did you go for VMMC services?	No because I'm already circumcised; No, Yes	1; 2; 3 (if No or Yes, go to Link_HIV_Care 19)
Link_HIV_Care 16	At what age were you circumcised?	< 5 years of age; XX years	
Link_HIV_Care 17	When were you circumcised?	MM/YYYY	
Link_HIV_Care 18	What was the main reason why you were circumcised?	Tradition or religious; To protect myself against HIV; Hygiene; Other medical reason; Other (specify); Don't know	1; 2; 3; 4; 5; 6
Link_HIV_Care 19	After being referred, did you attend the VMMC clinic?	No Yes	1; 2
Link_HIV_Care 17	Why did you decide not to attend the VMMC clinic after being referred?	The clinic is too far; The hours of the clinic don't suit me; I did not have transport to go the clinic; I'm not interested in VMMC;	1; 2; 3; 4;
Link_HIV_Care 16	If yes, did you decide to get circumcised?	No, Yes,	0; 1
Link_HIV_Care 17	If yes, where was the circumcision done?	Health facility Home of a health worker/professional Circumcision done at home Ritual site	1; 2;

		Other home/place Don't know	
Finish	We have now come to the end of our questionnaire. Thank you very much for taking part in this study.		

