### **7.3 Quantitative secondary distribution cohort data**

For the quantitative data arising from the secondary distribution cohorts, we will conduct analyses separately for the ANC and HIV testing and treatment cohorts. We will use descriptive analyses to describe the proportion of individuals accepting an offer of HIVST and the proportion who report that their partner used the HIVST. We will use standard logistic regression adjusting for study site to explore factors associated with accepting an offer of HIVST and with reported use of the HIVST.

Although the index individuals will be asked about linkage to care at 1-month follow-up, we will measure linkage to care using data from the intended users followed-up within 3-months after distribution. Linkage will be measured as the number of individuals reported to have linked to care (defined as accessing confirmatory testing services or attending an HIV care clinic for HIV-positive individuals or accessing VMMC services for HIV-negative males) among those who reported use of the HIVST.

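### The partner questionnaire has no linkage question for kit users who do not state a self-test result, although Section 7.3 keeps them in the linkage denominator

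*Protocol*

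**What the plan says.** Section 7.3 of the protocol fixes the source: "we will measure linkage to care using data from the intended users followed-up within 3-months after distribution". What counts as linkage is a confirmatory test, an HIV care visit by a positive user, or VMMC for a negative male, and the count is taken "among those who reported use of the HIVST". Secondary outcome 3 in Section 4.3.2 has a part a (use) and a part b (attending confirmatory testing, prevention or care within 3 months), both self-reported by the intended recipient. Objective 11 in Section 2.2 asks for the same information.

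The data come from the intended-user questionnaire in Appendix 3. One item asks "Did you use the HIVST kit", answered no or yes. Item M_HIV_Test_IU 8 then asks: "If you don't mind, what was the result of your HIV test using the test kit that you were given by your partner". It offers four answers: reactive, non-reactive, not known, and cannot disclose. The linkage items follow under two headings: "Section 6: Linkage to HIV care (Only for those who self-test HIV positive") and "Section 7: For partners reporting an HIV negative test result".

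Four other places bear on the point:
- The note at the start of Appendix 3 says the questionnaires are shown for their wording, and that response options, order and skip patterns may change on programming.
- The index follow-up form asks at about 1 month whether the partner went for confirmatory testing, HIV care or prevention.
- Section 7.4 says linkage data will rely primarily on the index individual.
- Section 5.4 says the intended-user linkage results are descriptive.

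**The concern.** The form invites a user to withhold the result, or to say it is not known, and then makes every linkage question depend on the result. Use and result are separate items, so a person can be a confirmed user with no stated result. That person may have gone for a confirmatory test or to a clinic, but the form has nowhere to record it.

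The linkage proportion is itself the output for objective 11 and outcome 3b, so incomplete capture goes straight into the reported figure. Section 4.4.2 also plans to combine service use reported in the cohort with unit costs to obtain the cost of linkage. Information that was never collected cannot be recovered in the analysis.

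**Working it through.** The protocol states no linkage rate, no expected share of undisclosed results and no sample size for linkage, so there is no planned figure to reproduce. The check is a trace of the form, followed by an illustration with assumed values.

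**Trace of M_HIV_Test_IU 8 for a partner who reports use**

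| Answer | Section 6 | Section 7 | Linkage asked? | In the Section 7.3 denominator? |
|---|---|---|---|---|
| 1 Reactive | yes | no | yes | yes |
| 2 Non-reactive | no | yes | yes | yes |
| 3 Not known | no | no | no | yes |
| 4 Cannot disclose | no | no | no | yes |

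Two of the four answers lead to no linkage item, and the form has no linkage item outside Sections 6 and 7. The wording carries the same restriction as the headings. The first item of Section 6 asks about going to confirm a positive self-test, and the first item of Section 7 asks about attending a clinic after an unreactive one. Neither can sensibly be put to someone whose result is unstated.

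**Size, under assumed values**

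Let u be the share of users who state no result, L the linkage rate among users who state one, and M the rate among those who do not. None of these is in the documents.

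- Recorded linkage, if unasked users count as not linked: L × (1 − u)
- True linkage: L × (1 − u) + M × u
- Shortfall: M × u, which is zero if M = 0 and u if M = 1

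With L = 50% and u = 20%:
- Recorded: 0.50 × 0.80 = 40%.
- True value if M = L: 0.40 + 0.50 × 0.20 = 50%.
- Range compatible with the record, M from 0 to 1: 40% to 40% + 20% = 60%.
- If unasked users are left out instead: 0.40 / 0.80 = 50%, which describes only users who state a result.

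Recorded linkage when M = L, for other assumed values:

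| True linkage | u = 5% | u = 10% | u = 20% | u = 30% |
|---|---|---|---|---|
| 30% | 28.5% | 27% | 24% | 21% |
| 50% | 47.5% | 45% | 40% | 35% |
| 70% | 66.5% | 63% | 56% | 49% |

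**The case against.** **The form is provisional.** The Appendix 3 note leaves response options and skip patterns open, and the draft is visibly unfinished (several linkage item numbers repeat). This stands in part: what is shown is a draft, not a committed procedure. But the questionnaires are presented for their wording, and the wording presupposes a result. Reprogramming the skips alone would not close the gap.

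**The bias needs a step that the protocol does not take.** Section 7.3 does not say that users with no linkage answer count as not linked, and an SAP may treat them as missing. This stands. A reader might infer that outcome 3b is certain to be understated; the documents do not support that. Treating these users as missing removes the mechanical deflation, but the figure then covers only users who state a result. The Section 7.3 definition also depends on status for HIV care and VMMC, so those two components cannot be classified under it when status is unknown.

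**The index form asks about partner linkage with no result condition shown.** Such linkage is therefore not wholly unrecorded by the study. But this is another person's report, at about 1 month, with a don't-know option. Outcome 3b is the intended recipient's own report within 3 months. Sections 7.3 and 7.4 disagree on the main linkage source and need reconciling in any case.

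**Who is lost is unknown.** A reader might infer that the loss falls mainly on men with reactive results, or differs between the ANC and HIV-positive cohorts. Nothing in the documents shows either. People who do not state a result may also link less often than others, which shrinks the shortfall, to nothing if none of them link. Nor is the interviewer sent by the partner: under Section 5.2 contact runs through the index individual, but the intended user gives verbal permission and then separate written consent.

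**Conclusion.** The gap in data capture is real in the form as drafted. Users who give either of the two non-stating answers belong to the Section 7.3 denominator and cannot be recorded as linked. Outcome 3b and objective 11 are understated if those users are counted as not linked; otherwise they are restricted to users who state a result.

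The size cannot be computed from the documents. The 40% recorded, with a compatible range of 40% to 60%, rests on two assumed values: 50% linkage and 20% of users not stating a result. No claim about which users withhold their result is needed or supported.

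The stakes are limited. The linkage results are declared descriptive, no power statement depends on them, and the primary outcome (partner use reported by the index patient) is untouched. This is a modest data-capture correction that is worth making.

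**What to change.** 1. Before Sections 6 and 7 of the intended-user form, ask every partner who used the kit, whatever the answer to M_HIV_Test_IU 8, whether he or she afterwards attended for (a) a confirmatory HIV test, (b) HIV care, or (c) VMMC or other prevention services.
2. Compute outcome 3b from these items, and report the number of users with no stated result alongside it. Say in Section 7.3 how the status-specific parts of the definition apply to them.
3. Add an invalid or could-not-read option to M_HIV_Test_IU 8. The index form already has an indeterminate category.
4. Keep Sections 6 and 7 for the result-specific detail.
5. Reconcile Sections 7.3 and 7.4 on whether the intended user or the index individual is the main source for linkage.

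The cost is three questions and one response option in the electronic form, plus a short text edit. No further participants or visits are needed, and a partner can report a clinic visit without stating a self-test result.
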